12.3 VITAL SIGNS

Blood Pressures and Heart Rate baselines are defined as the mean of values obtained from the last 6 weeks of screening including Day 1 prior to the first dose. For subjects on hemodialysis, pre-dialysis vital signs will be used. For subjects on peritoneal dialysis, vital signs may be recorded at any time during the visit.

Descriptive statistics for vital signs (e.g., systolic and diastolic blood pressure, MAP, heart rate, and respiratory rate) and their changes from baseline at each visit and at the end of study will be presented by treatment group.

Vital sign values are potentially clinically significant (PCS) if they meet both the observed value criteria and the change from baseline criteria listed in Table 6 below. The number and percentage of subjects with post-baseline PCS values will be tabulated by treatment group. The percentages are to be calculated relative to the number of subjects with baseline and at least one post-baseline assessment. The numerator is the total number of subjects with at least one post-baseline PCS vital sign value. Shift tables may be presented. A supportive listing of subjects with post-baseline PCS values will be provided including the patient ID, study center, baseline, and post-baseline values. A listing of all AEs for subjects with PCS vital signs will also be provided.

Table 7. Criteria for Potentially Clinically Significant Vital Signs

Vital Sign Parameter	Flag	Criteria*	
		Observed Value	Change from Baseline
Systolic Blood Pressure (mmHg)	High	≥ 170	Increase of ≥ 20
	Low	≤ 90	Decrease of ≥ 20
Diastolic Blood Pressure (mmHg)	High	≥ 100	Increase of ≥ 15
	Low	≤ 50	Decrease of ≥ 15
Pulse Rate (bpm)	High	≥ 120	Increase of ≥ 20
	Low	≤ 50	Decrease of ≥ 20
Weight (kg)	High	-	Increase of ≥ 10%
	Low	-	Decrease of ≥ 10%

*A post-baseline pre-dialysis or post-dialysis value is considered as a PCS value if it meets both criteria for observed value and change from pre-dialysis or post-dialysis baseline.

Additional analyses include but are not limited to

- Subgroup analyses of patients without any change in BP meds during treatment period
- Proportion of subjects meeting NKF BP target: within sBP 120-140 mmHg/dBP 70-90 mmHg at baseline, during treatment, and 4 weeks post treatment

12.4 ELECTROCARDIOGRAM (ECG)

Descriptive statistics for ECG parameters (e.g., Heart Rate, PR interval, QRS interval, QT interval, and QTc interval) at baseline and changes from baseline at each assessment time point will be presented by treatment group. QTc interval will be calculated using both Bazett ($QTcB = QT/(RR)^{1/2}$) and Fridericia ($QTcF = QT/(RR)^{1/3}$) corrections; and if RR is not available, it will be replaced with 60/HR in the correction formula.

A plot for each parameter of mean (+/- 95% CI) versus visit will be produced by treatment group (roxadustat vs. ESA).

ECG parameters values are potentially clinically significant (PCS) if they meet or exceed the upper limit values listed in Table 8 below. The number and percentage of subjects with post-baseline PCS values will be tabulated by treatment group. The percentages are to be calculated relative to the number of subjects with available non-PCS baseline and at least one post-baseline assessment. The numerator is the total number of subjects with at least one post-baseline PCS ECG value. Shift tables may be presented. A listing for all subjects with post-baseline PCS value will be provided including the patient ID, study center, baseline, and post-baseline PCS values.

In addition, a listing of all TEAEs for subjects with PCS ECG values and a listing of subjects with post-baseline significant ECG abnormalities as reported by the investigators will also be provided.

Table 8. Criteria for Potentially Clinically Significant ECG

ECG Parameter	Unit	Higher Limit
QRS interval	Msec	≥ 150
PR interval	Msec	≥ 250
QTc interval	Msec	> 500 ; Change from baseline > 60

12.5 OTHER SAFETY ANALYSES

A separate meta-analysis SAP for pre-specified, adjudicated composite safety endpoints to assess Cardiovascular, cerebrovascular and thrombo-embolic Events will be developed to complement this study specific SAP.

13 ADDITIONAL AND SUBGROUP ANALYSES

The analysis of the primary endpoints of US and EU, and Hb change from baseline to the average level during Week 18 to 24 may be performed separately by sex, age group, baseline iron replete status, baseline CRP group (\leq ULN vs $>$ ULN), and baseline stratification factors.

14 INTERIM ANALYSIS

Safety data and dosing decisions will be monitored on an ongoing basis. Additional ongoing review of safety data will be conducted by an independent DSMB (see protocol Section 3.7).

16 APPENDIX

16.1 APPENDIX 1: SCHEDULE OF ASSESSMENTS

Visit / Week:	Study Period:			Screening				Treatment			Follow-up	
	Up to 6 Weeks ^a			Day 1 (Wk 0)	Weekly (Wks 1 to 4) ± 2 days	Every 2 Weeks (Wks 6 to 24) ± 2 days	Every 4 Weeks (Wks 28 to EOT) ± 3 days ^b	EOT or ET ⁱ ± 3 days	EOS (4 wks post EOT or ET) ± 7 days			
	1	2	3									
Written informed consent	X											
Eligibility criteria	X			X								
Demographics and medical history	X											
Physical examination	X			X		Wks 12 ^c , 24 ^c		Wks 36 ^c , Q12wk ^{c, d}	X	X ^c		
Height, weight	X			X ^e				Wk 24 and every 24 wks ^e				
Blood pressure, heart rate, respiratory rate, temperature ^f	X	X	X	X	X	X	X	X	X	X		
Hemoglobin		X	X			X ^g		X ^g				
CBC with WBC differential	X			X	X	Wks 8, 12, 20		Wk 28, Q8wk	X	X		
Serum chemistry	X			X	Wk 2	Wks 8, 12, 20		Wk 28, Q8wk	X	X		
LFTs, CPK					Wk 2	Wks 6, 16						
Lipid panel (whenever fasting possible)	X			X	Wk 4	Wks 8, 12, 24		Wks 32, 40, 48, 60, Q24wk	X	X		
Serum iron, ferritin, TIBC, TSAT	X			X	Wk 4	Wks 8, 12, 20		Wk 28, Q8wk	X	X		
CHr	X			X	Wk 4	Wks 8, 12, 20		Wk 28, Q8wk	X	X		
HbA1c	X			X		Wk 12		Wks 28, 44, 60 Q16wk ^d	X	X		
Vitamin B ₁₂ , folate	X											
HIV ELISA, HBsAg, anti-HCV Ab	X											
Serum hCG pregnancy test	X ^h					Wks 12, 24		Wk 36, then Q12wks	X	X		
Reticulocyte count				X	Wks 1, 2	Wks 8, 20		Wk 44, Q24wk	X	X		
Special laboratory analytes (hepcidin, hs-CRP)				X	Wk 4	Wks 12, 20		Wk 44, Q24wk	X	X		
Optional archival serum/plasma samples				X	Wk 4	Wks 12, 20		Wk 44, Q24wk ^d	X	X		
HemoCue [®] assessment				X	X	X		X				
Quality-of-life questionnaires				X		Wk 12		Wks 36, 52 ^d	X			
12-lead ECG				X				Wk 24 and every 24 wks	X			
Renal ultrasound ⁱ		X										
Dose adjustment ^j					X	X	X					
Adverse event recording	X	X	X	X	X	X	X	X	X	X		
Concomitant medication recording	X	X	X	X	X	X	X	X	X	X		
Procedure and nondrug therapy recording	X	X	X	X	X	X	X	X	X	X		
Study drug dispensing ^k				X	X ^l	X	X					

Footnotes on following page

Abbreviations: Ab = antibody; BP = blood pressure; CBC = complete blood count; CHr = reticulocyte hemoglobin content; ELISA = enzyme-linked immunosorbent assay; EOT = End of Treatment; EOS = End of Study; ET = early termination; Hb = hemoglobin; HbA1c = glycated hemoglobin A1c; HBsAg = hepatitis B surface antigen; hCG = human chorionic gonadotropin; HCV = hepatitis C virus; HD = hemodialysis; HIV = human immunodeficiency virus; HR = heart rate; HRQoL = health-related quality of life questionnaire; HS-CRP = high-sensitivity C reactive protein; ICF = informed consent form; LFTs = liver function tests; PE = physical examination; RBC = red blood cell; RR = respiratory rate; SmPC = summary of product characteristics; TIBC = total iron binding capacity; TSAT = transferrin saturation; TX = treatment; WBC = white blood cells; Wk(s) = week(s); X = mandatory test/assessment.

- a Screening Hb values must be obtained at least 4 days apart.
- b Treatment duration is variable for each subject. All subjects will remain in the study treatment until up to 3 years after the last subject randomized.
- c Targeted PE only (e.g., respiratory and cardiovascular).
- d If the indicated assessments fall on a study treatment visit that is within two weeks of the planned EOT visit then these specified assessments can be postponed until the EOT visit.
- e Weight only (HD subjects: use dry weight).
- f Perform HR and BP at all week visits. Additional respiratory rate and temperature are measured at Day 1/Week 0 and EOT/ET.
- g Dedicated Hb sample for central lab should be collected during the visits where CBC is not collected.
- h Collect from female subjects of child bearing potential only.
- i A renal ultrasound examination will be performed during screening if no record of a renal imaging modality exists within 12 weeks prior to randomization.
- j Roxadustat subjects: Dose adjustments will be permitted from Week 4 onward, and every 4 weeks thereafter (except in extenuating circumstances) to correct and maintain subjects to a target Hb range. Please refer to dose adjustment rules as stated in **Error! Reference source not found.**
- Epoetin alfa subjects: Dose adjustments for HD subjects receiving epoetin alfa will follow the country specific product labeling for dosing and dose adjustments (e.g., PI; SmPC). For PD subjects, local standard of care may be followed for dosing and dose adjustments.
- k All assessments should be done prior to first study drug administration.
- l Dispense every other week
- m Subjects who prematurely discontinue study treatment will complete the ET and EOS visits, and – unless consent is withdrawn – will continue to be followed for CV events of interest, vital status and hospitalizations until study closure. These subjects will be asked to return for study visits every 3 to 6 months, or be available via telephone.

16.2 APPENDIX 2: DATA HANDLING CONVENTIONS

16.2.1 VISIT TIME WINDOW

Table 9 below presents the visits assigned for efficacy and safety analyses corresponding to the range of treatment days (window) during which an actual visit may have occurred.

Table 9. Analysis Visit Windows

Derived Visit	Scheduled Visit Day ^a	Window
Baseline, Week 0	Day 1	Days \leq 1
Week 1	Day 7*(Week #)+1	[Day 2, 10]
Weeks 2-3	Day 7*(Week #)+1	Days [Scheduled Day \pm 3]
Week 4	Day 7*(Week #)+1	[Scheduled Day -3, Scheduled Day +6]
Weeks 4-22	Day 7*(Week #)+1	[Scheduled Day -7, Scheduled Day +6]
Week 24	Day 7*(Week #)+1	[Scheduled Day -7, Scheduled Day +13]
Week 24 to xx	Day 7*(Week#)+1	[Scheduled Day -14, Scheduled Day +13]
ET	Earlier Termination, Match to a closest scheduled visit in protocol if patient had not been off drug for more than 7 days.	
EoT	Last assessment between Day 2 and EOT visit day, match to a closest scheduled visit in protocol if patient had not been off drug for more than 7 days.	
EoS (FU-4Wk)	Final visit for the Study 15 – 31 days after the last dose (excluding long term follow-up for early termination)	

^a: Relative to the first study medication date. For example, Day 1 = the first dose date of study medication.

Analysis Visit windows, as depicted in Table 10 below, will be used for the quality of life efficacy study assessments:

Table 10: Analysis Visit Windows for QoL

CRF Visit	Target Day ^a	Analysis Visit Windows Actual Assessment Day	Analysis Visit
Day 1	Day 1	Day 1	Baseline
Week 12	Day 7 * (Week #) + 1	[Target Day -14, Target Day + 27]	Week 12
Week 36	Day 7 * (Week #) + 1	[Target Day – 28, Target Day +27]	Week 36
Week 52	Day 7 * (Week #) + 1	\geq Target Day – 56, Target day + 83	Week 52
EOT Visit		Last assessment between Day 2 and EOT visit day, remapped to the closest next scheduled visit for HRQoL collection.	Week 12, 36, 52 and > 1 year

^a: Relative to Day 1 (first dose date of study medication)

Table 11. Analysis Visit Windows for Lipid Panel

Derived Visit	Scheduled Visit Day ^a	Window
Baseline, Week 0	Day 1	Days 1
Week 4	Day 7*(Week #)+1	[Day 2, 42]
Week 8	Day 7*(Week #)+1	[Scheduled Day -14, Scheduled Day +13]
Weeks 12	Day 7*(Week #)+1	[Scheduled Day -14, Scheduled Day +27]
Week 24	Day 7*(Week #)+1	[Scheduled Day -28, Scheduled Day +27]
Weeks 32-40	Day 7*(Week #)+1	[Scheduled Day -28, Scheduled Day +27]
Week 48	Day 7*(Week #)+1	[Scheduled Day -28, Scheduled Day +41]
Week 60	Day 7*(Week #)+1	[Scheduled Day -42, Scheduled Day +83]
Week 84 to xx	Day 7*(Week#)+1	[Scheduled Day -84, Scheduled Day 83]
EoT	Last assessment between Day 2 and EOT visit day, match to a closest scheduled visit in protocol if patient had not been off drug for more than 7 days	

^a: Relative to Day 1 (first dose date of study medication)

Visit Day is calculated by (visit date - date of first study medication + 1). If a patient has ≥ 2 actual visits within the same window, the last visit with non-missing value will be used for analysis.

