#### **6.1.2.6 Early Termination (ET)**

If a subject discontinues study medication permanently during the Treatment Period, perform the EOT assessments at the time of withdrawal from dosing or as soon as possible ([Section 6.1.2.5](#)). Erythropoiesis-stimulating agents may be started  $\geq$  3 days after the last dose of roxadustat.

Unless consent is withdrawn, these subjects will be followed up for CV events of interest, vital status, and hospitalization until study closure.

These subjects will be followed up every 3 to 6 months (depending on the availability of the subjects) until study closure. These visits may occur either in person or via telephone.

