#### **6.1.3 Post-Treatment Follow-Up Period**

##### **6.1.3.1 End of Study: 4 weeks ( $\pm$ 7 days) after EOT or ET**

- Laboratory tests:
  - Complete blood count with WBC differential
  - Serum chemistry
  - Lipid panel (fasting whenever possible)
  - Serum iron, ferritin, TIBC, TSAT
  - CHr
  - HbA1c
  - Reticulocyte count
  - Special laboratory analytes
  - Archival serum/plasma samples (optional donation, separate consent form)
- Targeted physical exam
- Serum hCG test for women of childbearing potential

- Blood pressure, HR
- Adverse event recording
- Concomitant medication recording
- Procedures and nondrug therapy recording

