### Appendix 3 Schedule of Assessments

Visit / Week:	Study Period:		Screening				Treatment		Follow-up	
	Up to 6 Weeks a		Day 1 (Wk 0)	Weekly (Wks 1 to 4) ± 2 days	Every 2 Weeks (Wks 6 to 24) ± 4 days	Every 4 Weeks (Wks 28 to EOT) ± 4 days b	EOT or ET ± 7 days	EOS (4 wks post EOT or ET) ± 7 days		
	1	2								
Written informed consent	X									
Eligibility criteria	X		X							
Demographics and medical history	X									
Physical examination	X		X		Wks 12 c , 24 c	Wks 36 c , Q12Wk c,d	X		X c	
Height, weight	X		X c			Wk 24 and every 24 weeks c				
Blood pressure, heart rate, respiratory rate, temperature f	X	X	X	X	X	X	X		X	
Hemoglobin		X			X g	X g				
CBC with WBC differential	X		X	X	Wks 8, 12, 20	Wk 28, Q8Wk	X		X	
Serum chemistry	X		X	Wk 2	Wks 8,12, 20	Wk 28, Q8Wk	X		X	
LFTs, CPK				Wk 2	Wks 6, 16					
Lipid panel (whenever fasting possible)	X		X	Wk 4	Wks 8, 12, 24	Wks 32, 40, 48, 60, Q24Wk	X		X	
Serum iron, ferritin, TIBC, TSAT	X		X	Wk 4	Wks 8, 12, 20	Wk 28, Q8Wk	X		X	
CHr	X		X	Wk 4	Wks 8, 12, 20	Wk 28, Q8Wk	X		X	
HbA1c	X		X		Wk 12	Wks 28, 44, 60 Q16Wk d	X		X	
Vitamin B 12 , folate	X									
HIV ELISA, HBsAg, anti-HCV Ab	X									
Serum hCG pregnancy test	X h				Wks 12, 24	Wk 36, then Q12 weeks	X		X	
Reticulocyte count			X	Wks 1, 2	Wks 8, 20	Wk 44, Q24Wk	X		X	
Special laboratory analytes (hepcidin, hs-CRP)			X	Wk 4	Wks 12, 20	Wk 44, Q24Wk	X		X	
Optional archival serum/plasma samples			X	Wk 4	Wks 12, 20	Wk 44, Q24Wk d	X		X	
HemoCue w assessment			X	X	X	X				
Quality-of-life questionnaires			X		Wk 12	Wks 36, 52 d	X			
12-lead ECG			X			Wk 24 and every 24 weeks	X			
Renal ultrasound i		X								
Dose adjustment j				X	X	X				
Adverse event recording	X	X	X	X	X	X	X		X	
Concomitant medication recording	X	X	X	X	X	X	X		X	
Procedure and nondrug therapy recording	X	X	X	X	X	X	X		X	
Study drug dispensing k			X	X l	X	X				

Footnotes on following page

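### SAP Table 9's End-of-Study window (days 15 to 31 after last dose) leaves out late but protocol-compliant End-of-Study visits and does not say where they go

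*SAP*

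**What the plan says.** **Analysis window.** SAP 16.2.1, Table 9, defines the EOS row, labelled as the 4-week follow-up, as the last study visit, held from 15 to "31 days after the last dose (excluding long term follow-up for early termination". The anchor is the last dose.

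**Visit schedule.** Protocol Appendix 3 sets the visit as "EOS (4 wks post EOT or ET) ± 7 days", and the heading of protocol 6.1.3.1 gives the same timing, counted "after EOT or ET". The schedule in SAP Appendix 1 carries the same EOS timing, so Table 9 also differs from another part of the SAP.

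**Gap between last dose and EOT/ET.** Protocol Appendix 3 gives this visit its own tolerance ("EOT or ET ± 7 days"). For subjects who stop treatment early, protocol 6.1.2.6 tells sites to "perform the EOT assessments at the time of withdrawal from dosing or as soon as possible". Neither fixes the number of days between last dose and the visit.

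**On-treatment weeks.** In Table 9, visits from Week 24 onward are windowed as "Scheduled Day -14, Scheduled Day +13", counted from first dose. A limit of 7 days off drug is stated in the ET and EoT rows only.

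**Use.** SAP 12.3 reports vital signs and their changes at each visit and at end of study. As an additional analysis it reports attainment of a blood-pressure target "at baseline, during treatment, and 4 weeks post treatment".

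**The concern.** An analysis window should capture the visits that the protocol tells sites to hold. This one uses a different anchor and closes early. It allows 13 days before the 4-week point (28 − 15) and only 3 days after it (31 − 28), whereas the protocol allows 7 on each side. A site can follow the protocol exactly and still produce an EOS visit that the SAP does not recognise as EOS.

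The SAP does not say what then happens to that visit. Because the on-treatment rows run on without an off-drug limit, a literal program could give it a treatment-week label.

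EOS is the only scheduled post-treatment visit with laboratory tests, blood pressure and heart rate; later follow-up of early terminators (protocol 6.1.2.6) covers cardiovascular events, vital status and hospitalization. At stake are the completeness of the end-of-study summaries and the purity of the on-treatment by-visit safety summaries.

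**Working it through.** **Inputs**

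- Protocol EOS window: 28 ± 7 = days 21 to 35 after EOT/ET (protocol 6.1.3.1, protocol Appendix 3, SAP Appendix 1).
- SAP EOS window: days 15 to 31 after last dose (SAP Table 9).
- Lag L = EOT/ET date minus last-dose date. The documents do not give it, so it is treated as an assumption and varied from −7 to +7 days.

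**Can the SAP window be reproduced from the schedule?** No. The protocol window holds 35 − 21 + 1 = 15 days and the SAP window 31 − 15 + 1 = 17 days, so no value of L turns one into the other.

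**Which compliant visits fall outside?** Counted from last dose, compliant EOS visits fall on days 21 + L to 35 + L. For L from −4 to 7, the number of allowed days beyond day 31 is (35 + L) − 31 = L + 4. An on-target visit falls on day 28 + L and is outside once 28 + L > 31, that is L ≥ 4.

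| Lag L (days) | Compliant days after last dose | Allowed days outside 15–31 | On-target visit |
|---|---|---|---|
| −7 | 14–28 | 1 of 15 (day 14) | day 21, inside |
| −6 to −4 | 15–29 to 17–31 | 0 of 15 | inside |
| 0 | 21–35 | 4 of 15 (days 32–35) | day 28, inside |
| 3 | 24–38 | 7 of 15 | day 31, inside |
| 4 | 25–39 | 8 of 15 | day 32, outside |
| 7 | 28–42 | 11 of 15 | day 35, outside |

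When L is zero or more, no compliant visit can occur on days 15 to 20, so that part of the SAP window is unused.

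**Where would a late visit go?** Take last dose and EOT on Day 365 and EOS 33 days later, on Day 398. The visit is compliant (33 lies between 21 and 35) and misses the EOS row (33 > 31). The Week 56 scheduled day is 7 × 56 + 1 = 393, with window 393 − 14 = 379 to 393 + 13 = 406. Day 398 lies inside it. Nothing in that row excludes a value taken 33 days off drug.

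**Check of the proposed rule.** With the window set at 21 to 35 days after EOT/ET, 0 of the 15 allowed days fall outside, whatever the lag.

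**The case against.** The strongest reply has four parts.

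1. **Only the late tail is affected.** At zero lag, 11 of 15 allowed days are kept, and an on-target visit is kept at lags of 0 to 3 days. This stands. So does the related point that the EOT tolerance is two-sided: if a dose follows the EOT visit, fewer or no late visits are lost.

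2. **Treatment-week labelling is one reading, not a stated rule.** Table 9 introduces its windows as ranges of treatment days, and a day 33 days off drug is arguably not one. The grouping rule in SAP 5.4 concerns unscheduled visits, and EOS is scheduled. This stands in part: the SAP is silent on a late final visit. Silence still leaves the programmer to choose, and the table as written does not prevent the wrong choice.

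3. **The data are not lost.** SAP 16.2.2 uses every post-baseline assessment to determine potentially clinically significant values and lists all assessments. Treatment-emergent adverse events are classified by date (SAP 12.1.1). This stands, and it limits the point to descriptive summaries. The further rule in 16.2.2, that the last post-baseline value serves as end of study, covers repeated or unscheduled assessments; it does not settle a single scheduled visit on day 32.

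4. **Anchoring to last dose measures time off drug directly.** True, but it does not explain closing at day 31. Reporting days since last dose keeps that benefit.

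Two stronger readings are tempting. A reader might turn the day counts into percentages of visits lost; that would require visits spread evenly over the 15 days and a known lag, and the documents give neither. A reader might also infer selective loss in early terminators. Protocol 6.1.2.6 permits their ET visit to lag the last dose, but does not establish that it does, still less by 4 or more days.

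**Conclusion.** The mismatch is real and follows from the documents alone. Table 9 uses a different anchor and range from the protocol and from the SAP's own schedule. Compliant EOS visits on day 32 or later after last dose fall outside the EOS row: 4 of 15 allowed days at zero lag, and the on-target visit too at lags of 4 days or more. These are counts of allowed calendar days, conditional on an assumed lag, and not estimates of how many subjects are affected. Assignment to a treatment week is what Table 9 permits when read literally; it is not an instruction.

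The effect shown is confined to descriptive by-visit and end-of-study laboratory and vital-sign summaries, and possibly the 4-weeks-post-treatment blood-pressure item, since SAP 12.3 does not say whether that item uses the Table 9 row. Determination of potentially clinically significant values, listings and treatment-emergent adverse events are not shown to be affected.

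A reader might go further and infer that an early terminator's late EOS hemoglobin enters the Week 28 to 52 efficacy average. The documents do not establish this. The SAP never says that an EOS value is used there, and gives no count of such visits. No effect on the efficacy hypotheses is shown, and sample size, power and alpha are untouched. Severity is minor.

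**What to change.** In SAP 16.2.1, Table 9:

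1. Define EOS as the nominal EOS visit, or as an assessment 21 to 35 days after the EOT/ET visit, matching protocol 6.1.3.1 and both schedules.
2. Report days since last dose alongside the EOS summaries, so that time off drug stays visible.
3. In the by-visit safety summaries, apply the 7-day off-drug limit already stated in the ET and EoT rows to the scheduled-week rows as well, so that a post-treatment value cannot carry a treatment-week label.

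It would also help to state in SAP 12.3 whether the 4-weeks-post-treatment blood-pressure item uses this EOS definition.

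The cost is SAP wording and a programming change. No new data, visits or protocol amendment are needed.

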The mean change from baseline at weeks 12, 36, and 52 weeks will be computed for each treatment group. A paired t-test will be used to assess within treatment effect. Between treatment difference will be assessed using the MMRM model with baseline sub-score as a covariate, and treatment group, visit, interaction of treatment and visit, and stratification factors as fixed effects. The same strategy as that used in MMRM in Section 11.1.3.1 will be used to choose variance covariance. Data up to visit of Week 52 will be included in the analyses. Non-inferiority of roxadustat vs. ESA will be tested. The non-inferiority margin is fixed as a difference of 2 points.

HRQoL benefit will also be assessed using SF-36 vitality and physical functioning subscales. Mean change in following endpoints at above-mentioned time points will be analyzed and compared between the 2 treatment groups using MMRM using the baseline value as a covariate, treatment group, visit, the interaction of treatment and visit, adjusting for the stratification factors. The same strategy as that used in MMRM for Hb will be used to choose variance covariance structure. Other than below endpoints for exploratory analyses, other QoL variables may be performed

- Vitality Subscale of SF-36: In FAS subjects with baseline Vitality Sub-score below 50.
- Physical Component Scores of SF-36:
 - In FAS subjects with baseline *physical component scores* below 40.
 - In all FAS subjects.
- Anemia Subscale (“Additional Concerns”) of Functional Assessment of Cancer Therapy-Anemia (FACT-An) Scores:
 - In FAS subjects with baseline subscale scores below 55 (generally associated with fatigue).
 - In all FAS subjects.
- Total FACT-An Scores:
 - In FAS subjects with baseline FACT-An scores below 135
 - In all FAS subjects.
- EQ-5D-5L Scores: In all FAS subjects.

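### SAP Table 10 moves end-of-treatment quality-of-life scores forward to the next scheduled visit with no limit on distance or time off drug, so some scores are analysed as Week 36 or Week 52 values although taken months earlier

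*SAP*

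**What the plan says.** SAP Section 16.2.1, Table 10, gives three numeric windows for quality-of-life forms: Week 12, "Target Day -14, Target Day + 27"; Week 36, "Target Day – 28, Target Day +27"; Week 52, "Target Day – 56, Target day + 83". A further row covers the EOT visit: "Last assessment between Day 2 and EOT visit day, remapped to the closest next scheduled visit for HRQoL collection". The visits it can feed are "Week 12, 36, 52 and > 1 year".

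The EoT rows of Table 9 (general assessments) and Table 11 (lipids) read differently: "match to a closest scheduled visit in protocol if patient had not been off drug for more than 7 days". The ET row of Table 9 carries the same condition.

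Protocol 6.1.2.5 schedules SF-36, FACT-An and EQ-5D-5L at EOT. Protocol 6.1.2.6 has EOT procedures done when a subject stops study drug early, or as soon as possible after that. The Table 10 EOT row therefore governs early discontinuations as well as planned completions.

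SAP 11.3.8 analyses change from baseline at Weeks 12, 36 and 52 by MMRM, and adds: "Non-inferiority of roxadustat vs. ESA will be tested. The non-inferiority margin is fixed as a difference of 2 points".

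**The concern.** An MMRM takes the visit label as the time of measurement. Table 10 lets that label differ from the actual time by months, and only for subjects who reached EOT before the labelled visit. The instruments cannot cover such a gap: FACT-An asks about the past seven days (Protocol 6.7.2), and many SF-36 items ask about the past four weeks (SAP Appendix 4).

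Two further gaps make the rule hard to program in only one way. The table does not rank the EOT row against the window rows, although the two can send the same form to different visits. And the row's reference to the last assessment since Day 2 could be read to pick up an earlier scheduled form when none was completed at EOT.

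The missing off-drug limit also matters. Protocol 6.1.2.6 allows ESA treatment to begin 3 or more days after the last roxadustat dose, so a late EOT form could reflect a different treatment yet count as an on-arm score.

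At stake are the between-arm HRQoL comparisons at Weeks 36 and 52, for patient-reported outcomes in an open-label trial. If the timing or frequency of stopping differs by arm, the arms are compared at different real times under one visit label.

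**Working it through.** The plan states no figure on this point to reproduce. The check is to work out which visit each possible EOT day is given.

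**Inputs (SAP Table 10).** Target day = 7 × week + 1. I read each window as inclusive at both ends.

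- Week 12: target 7 × 12 + 1 = 85; window 85 − 14 = 71 to 85 + 27 = 112.
- Week 36: target 7 × 36 + 1 = 253; window 253 − 28 = 225 to 253 + 27 = 280.
- Week 52: target 7 × 52 + 1 = 365; window 365 − 56 = 309 to 365 + 83 = 448.

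The windows leave Days 2-70, 113-224 and 281-308 uncovered.

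**Reading A: windows first, EOT row only for uncovered days.** Days early = target day − EOT day.

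| EOT day | Analysed as | Days early |
|---|---|---|
| 2-70 | Week 12 | 85 − 70 = 15 to 85 − 2 = 83 |
| 113-224 | Week 36 | 253 − 224 = 29 to 253 − 113 = 140 |
| 281-308 | Week 52 | 365 − 308 = 57 to 365 − 281 = 84 |

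**Reading B: EOT row first.** The earliest day whose next visit is Week 36 is Day 86, and 253 − 86 = 167 days. The earliest day whose next visit is Week 52 is Day 254, and 365 − 254 = 111 days.

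The maxima for Weeks 36 and 52 must be taken as pairs: 140 and 84 under A, 167 and 111 under B.

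**Where the rows disagree.** On Days 86-112 the window gives Week 12 and the EOT row Week 36. On Days 254-280 the window gives Week 36 and the EOT row Week 52. That is 27 + 27 = 54 days with two possible answers. EOT days after 365 are left out, because the table gives its category beyond one year no target day or window.

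**Example of the conflict.** Footnote d of the schedule lets the Week 36 questionnaire be postponed to a planned EOT visit within two weeks. Completed on Day 253 + 14 = 267, it lies inside the Week 36 window. The EOT row would send it to Week 52, 365 − 267 = 98 days early.

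**Comparison with a nearest-visit rule, as in Tables 9 and 11.** The midpoint of Days 85 and 253 is Day 169, and that of Days 253 and 365 is Day 309. The earliest day nearest to Week 36 is therefore 170 (253 − 170 = 83 days early). For Week 52 it is 310 (365 − 310 = 55 days early).

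**Effect on the contrast, on assumed inputs only.** Let f be the share of an arm's values at a visit that were moved forward. Let d be the mean difference between a moved score and the same subject's score at the labelled visit, taken as equal in both arms. The bias in the difference is (f₁ − f₂) × d. With 15-20% against 10%, and d of 2 to 10 points, it runs from 0.05 × 2 = 0.1 to 0.10 × 10 = 1.0 point. With equal shares it is 0. None of these inputs comes from the documents.

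**The case against.** **Precedence is not stated.** A reader might infer that the EOT row overrides the windows, so that a form from Day 100 certainly becomes Week 36. The text introducing Table 10 says only that its windows will be used. The override is one reading, so the verdict rests on Reading A.

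**Carry-forward is not certain.** A reader might infer that a Week 12 form is re-used as Week 36 whenever no EOT form exists. The wording allows that, but the row is keyed to the EOT visit and does not say so. The same reference to the last assessment since Day 2 appears in the EoT rows of Tables 9 and 11.

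**Tables 9 and 11 are not a complete model.** Their nearest-visit rule has no maximum distance either, and it would still move quality-of-life scores by up to 83 and 55 days. This stands: copying that rule would shorten the shift without removing it. The 7-day off-drug difference is real.

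**A bias of a stated size does not follow.** It is tempting to multiply a difference in stopping rates by the gap between stoppers and continuing subjects and call the product bias. That gap is not the timing error. If stoppers stay low, a moved score may be nearly right, and leaving it missing makes the MMRM borrow from continuing subjects. This stands, and it makes the choice partly a trade-off. The stated endpoint also averages Weeks 12, 36 and 52 (SAP 4.4), so under equal weights a shift at one visit enters at one third of its size.

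**Reasons for stopping are unknown.** Protocol 6.1.3.2 lists reasons without frequencies. Treatment may be shorter than 52 weeks by design (Protocol 3.1), so some early EOT forms will be administrative.

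**Conclusion.** The point holds. Even on the reading kindest to the plan, EOT questionnaires from Days 113-224 enter the model as Week 36, 29-140 days early, and those from Days 281-308 as Week 52, 57-84 days early. Forms from Days 2-70 enter as Week 12, 15-83 days early. If the EOT row prevails, the maxima rise to 167 days for Week 36 and 111 days for Week 52. The upper figures are maxima; a form completed just before a window opens moves about 4 weeks (Week 36) or 8 weeks (Week 52).

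The day counts rest only on the Table 10 formulas and inclusive windows. The size and direction of any bias in the treatment difference cannot be computed from the documents, and it could be close to zero if stopping is balanced.

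A reader might infer a threat to the trial's main conclusions; the documents do not support that. HRQoL is an additional efficacy evaluation (SAP 4.4 and 11.3.8), outside the fixed sequence in SAP Table 5. The correction should still be made, because a formal 2-point non-inferiority comparison would otherwise rest on mislabelled assessment times and a rule that two programmers could implement differently.

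**What to change.** Rewrite the EOT row of SAP Table 10 to say:

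- The EOT or ET questionnaire is assigned by its actual assessment day using the Week 12, 36 and 52 windows, and the windows take precedence.
- It is assigned only if the subject has been off drug for no more than 7 days, as in Tables 9 and 11.
- No questionnaire is used for two visits. If two forms fall in one window, the last-value rule already given in Section 16.2.1 applies.
- A form outside every window is summarised as EOT only, and the scheduled visit is left missing in the MMRM.

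The change is to one table row. The cost is fewer observed values: EOT forms from Days 2-70, 113-224 and 281-308 leave the model. Subjects who stop before Day 71 then have no post-baseline quality-of-life value in it, since Week 12 is the first scheduled collection. Because that is a real loss, the present next-visit mapping can be kept as a sensitivity analysis, with its precedence and re-use rules written down.
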